5.3 Informed Consent Procedures

Consent will occur in two phases: Initial verbal consent for telephone screens. Full written informed consent during baseline assessment.

Verbal consent during phone screen. At the beginning of the phone screen for each partner, the research assistant conducting the screening will describe the study and all aspects of consent to the patient and evaluate comprehension of consent using two comprehension questions (*Doc#10*). Conducting this first assessment separately allows each partner to ask individual questions of the researcher without concern for embarrassment in front of their partner in addition to increasing privacy/confidentiality during the actual screening process.

For participants who are mailed recruitment letters, the mailer will include a sample of the consent form as well as the Notification of Privacy Practices for non-Veteran participants so that they will additionally be able to review these documents. Participants who receive a recruitment letter from their provider directly will be able to request a copy of the letter during their phone interview and will be able to request a call back at a later date to give them time to review the information.

We are requesting a waiver of consent documentation for this phone screening (*Doc#11*); full written informed consent will take place at the Baseline Assessment for those participants who are eligible following the phone screen and wish to participate in the Baseline Assessment.

Full consent during baseline assessment. At the beginning of the baseline assessment for each partner, the research assistant conducting the assessment will review the written consent document with the participant (Doc#12), describing all aspects of consent. We will evaluate comprehension of consent using additional comprehension of consent questions. As couples psychotherapy requires full involvement of all participants, potential subjects who appear to have impaired decision-making ability or difficulty comprehending the consent will not be enrolled in the study. Concerns will be discussed with Drs. [name] or [name], licensed psychologists who will integrate findings to determine whether exclusion criteria are met.

During the non-Veteran partner's consent process, they will additionally be presented with a notification of Privacy Practices and will be asked to sign the acknowledgment of Notification of Privacy Practices (*Doc#30*).

Participants completing the baseline over the phone will be asked to provide verbal consent, as well as complete the required baseline documents (consent; HIPAA authorization; and notice of privacy practices for partners without a VA record). The interviewer will document the verbal consent as well as satisfactory demonstration of comprehension of consent on the new Baseline comprehension of consent document (*Doc#33*). We will continue with the baseline questionnaires and interview upon receiving verbal consent. However, no follow-up activities (chart review; documentation in the medical record; scheduling sessions) will occur until we have received fully signed consent forms, HIPAA authorizations forms and acknowledgment of Notification of Privacy Practices from any non-Veteran partners in the mail.

Training. All staff obtaining consent have completed required CITI trainings regarding human subjects requirements. Staff obtaining and documenting informed consent (1) will be trained by the PI and study-coordinator, (2) will roleplay the consent process with the PI and study coordinator, and (3) will be observed in their first phone assessments and baseline assessments until the PI is satisfied that they can independently describe all aspects of consent and adequately assess comprehension of consent.

5.4 Inclusion/Exclusion Criteria

List of criteria for inclusion

- 1) Both partners must be age 18 or over
- 2) Both partners must demonstrate sufficient knowledge of English and cognitive capacity to understand the study through comprehension of consent questions
- 3) Both partners must self-identify as "in a committed relationship" with their partner for at least 6-months.
 - *Note:* Eligibility will NOT be based on marital/cohabitation status or sexual orientation to remain consistent with VA priorities of offering inclusive family services.
- 4) At least one partner must report at least mild relationship distress on a satisfaction screen (CSI-4<13.5)
- 5) At least one partner must have Veteran status
- 6) The Veteran partner must screen positive on at least one PC-Screen (i.e., PHQ-2 ≥3; PHQi9≥1; AUDIT-C≥5; OR PC-PTSD-5≥4)

List of criteria for exclusion:

- Either partner reports that they are engaged in ongoing couple or family therapy (via brief questions during Telephone Screen).
 Note: Any new couple/family therapy scheduled *after* screening will not impact eligibility and will be evaluated as an outcome.
- 2) Either partner reports severe intimate partner violence in the last year (via semi-structured interview during the Baseline session).
- 3) Either partner reports experiencing suicidal intent / attempts in the last month (via C-SSRS in Baseline session).
 - *Note:* Participants will NOT be excluded based on suicidal ideation or plan alone.
- 4) Either partner experiences current psychosis (via chart review, presentation during session, or MINI psychosis scale).
- 5) Either partner experiences current mania (via chart review, presentation during session, or MINI mania scale).

All staff will be trained in the semi-structured IPV interview, C-SSRS, P4, and MINI psychosis and mania scales to be used at any time they are concerned about individual functioning during either in-person sessions or phone sessions. Veteran charts will be reviewed prior to any Veteran-participants' to check for any indications of hospitalization or records flag. Results will be discussed with Drs. [name] or [name], licensed psychologists who will integrate findings to determine whether exclusion criteria are met.

5.5 Study Evaluations

Questionnaires

See Table 1 for full list of measures. Except for newly developed measures, all measures have established reliability/validity and were selected with preference for measures used in VHA care.

Inclusion/Exclusion. The listed measures will assess eligibility (per Section 5.4). The relationship quality screen and PC-Screens are established short forms used in VA practice.

Safety. In addition to routine use to evaluate exclusion measures

Outcomes (Aim 2). We selected measures of relationship quality and depression used in weekly assessments for VA EBPs.²⁶ Intimacy and interpersonal risk will be assessed using well-validated measures. We are piloting new measures about communication around mental health.

Evaluation (Aim 3). The well-established acceptability measures are supplemented with open-ended interview questions to identify unique strengths and weaknesses of the program *Risk.* Measures assess shared risk factors for suicide and divorce to contextualize findings.

Table 1List of Measures used in Study										
Construct	Measure	Items	Purpose	Screen	Base	Tx	Post			
Demographics	Standard Items	8	Inclusion	X						
Relationship Status	Made for Study	4	Inclusion	X						
Tx Engagement	Made for Study	6	Exclusion	X						
Veteran Status	Standard Items	5	Inclusion	X						
IPV Assessment	VA IPV Screen	8	Safety		X		Xa			
Severe IPV Behaviors	IPV Interview	8	Exclusion/Safety		(X)	(X)	(X) ^a			
IPV Monitoring	IPV Session	1	Safety			Х				
Mania/Psychosis	MINI ²⁵	20	Exclusion		(X)	(X)	(X)			
Last Month Suicide Ideation Severity	C-SSRS ²⁷	5	Exclusion/ Safety		Х		Х			
Suicide Risk Eval	P4 Screener	4	Safety	(X)	(X)	(X)	(X)			
Relationship Quality	CSI ²⁸	4/32	Aim 2-1	Xb	Х		Х			
Intimacy	PRI	16	Aim 2-1		Х		Х			
Recent (2-Week) Depression	PHQ-9 ²⁹	2/8	Aim 2-2	Xp	Х		Х			
Recent Suicidal Ideation	PHQ-i9 ²⁹	1	Aim 2-2	X	Х		Х			
Last Month Ideation Intensity	C-SSRS ²⁷	5	Aim 2-2		X		Х			
Interpersonal Connection	INQ ³⁰	15	Aim 2-2		X		Х			
Discussing Mental Health	Made for Study	18	Aim 2-3		Х		Х			
Service Utilization	Chart Review	N/A	Aim 2-3				Х			
Perceived Quality of Service	CSQ-18 ³¹	8	Aim 3-1				Xa			
Quality of Alliance w/ Provider	WAI-SR ³²	12	Aim 3-1				Xa			
Semi-Structured Interview	Made for Study	15	Aim 3-2				Х			
Potential PTSD	PC-PTSD-5 ³⁴	6	Inclusion	X						
Trauma Exposure	LEC-5 ³⁵	17	Risk		X					
Childhood Adversity	ACES ³⁶	17	Risk		X					
PTSD	PCL-5 ³⁷	20	Risk		Х		Х			
Lifetime suicide ideation, lifetime/last-month attempts	C-SSRS ²⁷	20	Risk/Safety		Х		Х			
Disordered Drinking	AUDIT ³³	3/10	Inclusion/Risk	Xb	Х					
Drug Abuse	DAST-10 ³⁸	10	Risk		Х					
Last month alcohol / drug use	AUDADIS ³⁹	20	Risk		Х		Х			
^a Modified for study. ^b Phone screen will use established short-form versions.										

Chart Review

A post-treatment chart review of a Veteran partner's chart will be used to evaluate engagement in mental health services over the following windows: 1) 90-day period prior to the baseline session; 2) during the treatment period from baseline to the day of the final feedback session, 3) the 90-day period after the final intervention session. Over each window, staff will review treatment appointments (e.g., individual, group, assessments), consults placed (e.g., General Mental Health; MST coordinator); and new prescriptions (e.g., Naltrexone; SSRIs).

5.6 Data Analysis

Sample Size Determination

As the purpose of the present study is to primarily pilot the BRC intervention, we selected our target sample size based on our maximum expected capacity to run subjects through the protocol given our limited staff (2 couples/month) and the limited time in which to run the study (1 year).

Expected study continuation/lost to follow-up rate. We project 75% retention based on prior VA RCTs with couples.^{39,40} Thus, if we successfully recruit 20 couples, we expect to obtain complete data from 15 couples at follow-up.

Expected screen failures. As noted above, we expect that only 20% of Veterans screened will be both eligible and interested in participating in the larger study and that only 50% of partners will be eligible and interested. Thus, we are expecting 200 screen failures (i.e., approximately 160 Veterans and 40 Non-Vet partners).

Analytic Strategy by Aim

The Drs. [name] and [name] will maintain the database and conduct all analyses. Findings will be used for the preliminary study sections of a grant and, depending on data, in presentations or publications.

Aim 1: Evaluate the feasibility of BRC. Frequencies will be used to calculate the recruitment rate (i.e., # couples where both agree to attend the baseline/30-day period; Sub-aim 1-1) and completion rate (i.e., # completing all sessions/those completing baseline; Sub-aim 1-2). The above metrics will be calculated both across the sample and within recruitment source to estimate the feasibility of conducting a large-scale RCT in that population. To evaluate protocol adherence (Sub-aim 1-3), staff other than the therapists will evaluate randomly selected digital session recordings from each therapist using established criteria that rates elements of BRC delivery on a 1-5 scale.²⁶ Sufficient adherence is defined as 75% of elements rated at 4 or higher.

Aim 2: Pilot outcomes. As relationship quality and emotional intimacy are dependent between partners, we will calculate effect size dyadically using a repeated measures ANOVA with Partner (Veteran-Supporting) and Time (pre-post) as within "subjects" factors to generate partial-η² (Sub-aim 2-1). In contrast, differential recruitment criteria will create baseline differences in suicide risk factors (Sub-aim 2-2) and efficacy discussing mental health (Sub-aim 2-3). Thus, we will calculate separate Cohen's *d* estimates for Veteran and Supporting partners. Effect sizes will then be contrasted with 1-month change in the above outcomes observed in past waitlist control studies of Veterans to inform power analysis. Finally, we will examine chart review data to investigate change in proportion of Veterans engaged in mental health services (Sub-aim 2-3). In cases where specific referrals were made in the final session, we will also assess the proportion utilizing those services.

Aim 3: Explore suitability of BRC. Mean scores will be calculated for each participant on the CSQ-8 and the WAI. Acceptability (Sub-aim 3-1) is defined as 75% of participants scoring ≥3 on both measures. We will use framework-guided rapid analysis (RA) to evaluate semi-structured interviews.⁵⁸ Transcription services will be provided through VA HSR&D's Centralized Transcription Service Program (CTSP). The audio recordings to be transcribed by CTSP staff will not contain any identifiable information and will only be labeled with a study identification number. They will be saved in a project folder shared between IRB-approved study staff and CTSP transcription staff that is located on the VA secure V: drive. IRB-approved study staff will place the audio files into the shared folder for a CTSP transcriptionist to have access for the purposes of transcription. Once the audio file is transcribed, the transcriptionist will save the completed transcript in the same shared folder using the same identification number. No data (audio files, in process transcripts, or completed transcripts) will leave the VA secure server. As

completed transcripts become available, approved study staff will move these files from the transcription folder into another folder that is only accessible to IRB-approved study staff and password protected, where they will be stored for qualitative analysis. RA templates will summarize transcripts on specific BRC elements. These will be consolidated into themes that can inform BRC refinement (Sub-aim 3-2). RA yields insights comparable to more intensive coding using less staff resources.⁵⁸

Exploratory analyses. Due to a lack of prior literature on relationship-focused interventions impacting risk factors beyond depression, we do not have any specific aims or directional hypotheses. However, we will calculate separate Cohen's *d* estimates by partner using the same analytic approach seen in Sub-aim 2-2. Additionally, we will compare outcomes across higher and lower-functioning couples. The analyses will help evaluate the BRC's tolerability and safety, adding additional considerations for changes in the RCT.

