Session 3: Feedback. The final session is framed around a review of the automatically generated report with the couple, addressing history, strengths, and concerns in sequence. The bulk of session time is spent on the "menus" presented for each concern. Using an MI framework, the therapist helps partners select relevant options or generate their own. Throughout the discussion, the therapist will help partners address barriers towards implementation and offer VA resources and referrals to support partners' decisions. For couples completing Session 3 remotely, this report will be mailed at the end of the session along with follow-up questionnaires.

Training & Supervision. All interventionists will be master-level psychology graduates or psychology postdocs and will be trained by consultants [name] (BRC developer) and [name] (BRC master trainer) in an 8-hour session reviewing the BRC protocol and demonstrating skills for managing couples and encouraging relationship-promoting views of problems.

All study sessions will be recorded using approved digital recorders or secure voice recording software installed on VA computers. BRC delivery will be supervised in weekly meetings with the [name] (PI) and [name] (Co-I), who are experienced in MI ([name]) and couple therapy including BRC ([name]) with Veterans. All staff will be trained in risk assessment by [name] and risk management will be supervised by [name] and [name] (Co-I), licensed psychologists who have served as PIs on high-risk Veteran studies.

Follow-up assessment.

Follow-up Questionnaire Packet (Doc#19). At the end of the final treatment session, staff will hand partners paper copies of the questionnaires (or mail the packet to them in case of remote sessions) to either (1) complete directly after the session if they wish, (2) mail back to study staff with pre-stamped envelopes, or (3) to have as a reference when completing the questionnaires remotely in the final interview. This is designed to maximize convenience for couples. If study staff have not received the packet by 1-week (or after their scheduled final interview), study staff will send reminder calls to participants to remind them to complete the packet or to offer them the opportunity to complete these questions by phone.

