Follow-up Semi-structured Interview (Doc#20). After the final treatment session, partners will be asked to schedule separate follow-up interviews with study staff between within 30 days of the final treatment session. Interview will consist of an open-ended treatment evaluation, suicide ideation assessment, and IPV assessment (modified to a 1-month timescale). As above, this can be completed remotely or in-person based on participant convenience

After completing the final interview and questionnaire, participants will be thanked, final payments will be made, and no further contacts will be scheduled. Participants who request further treatment will have any requested consultations scheduled. Participants that share any risk concerns (i.e., new violence over the prior month; any ideation with intent over the prior month) will be immediately referred to appropriate resources for follow-up.

Risk benefit analysis

Anticipated benefit. Participants may experience indirect benefits of study participation. As part of the check-up process, participants will be thoroughly screened for individual mental health concerns and relationship concerns and will be offered treatment recommendations and referrals, which may lead to concerns being addressed in treatment.

Prior research in civilian couples and active duty Airmen suggest that participating in the BRC intervention sessions may lead to direct improvements for relationship quality for some couples, however we cannot guarantee that any direct benefit will be experienced by the couples in our study.

Dissemination of the findings from the study will contribute to the extant literature, provide data to guide a larger trial, and may contribute to knowledge about ways to better support well-Veteran relationships.

Population risk. The purpose of this project is to pilot a brief intervention with Veterans screening positive for known suicide risk factors (i.e., depression, alcohol use, PTSD, suicide ideation) and known IPV risk factors (i.e., relationship distress, alcohol use, PTSD). Thus, participants will be at a somewhat elevated risk for suicidal crises, intimate partner violence, and other negative outcomes.

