5.7 Withdrawal of Subjects

Voluntary withdrawal

Process for withdrawal. All couple-based treatment sessions will require consent from both partners before proceeding. Individual participants may request to withdraw from participating in the study at any time by contacting study staff. Study staff will ask for a brief reason for voluntary withdrawal to monitor for potential adverse events. If staff is concerned about safety, they will conduct follow-up assessments as appropriate based on their concerns (e.g., IPV interview, P4 suicide risk screener, MINI mania/psychosis screen) and follow the appropriate protocol.

Withdrawal of one partner during treatment. As this is a pilot of a couples treatment, if either partner withdraws during the treatment process, then the other partner will not be able to complete the treatment. Partners will be reminded of this fact and will be offered the opportunity to withhold their decision to withdraw if they would like to discuss their choice with a partner first (with a member of study staff following up after participating). However, partners are NOT REQUIRED to take this time in order to withdraw.

If a participant withdraws while the couple has an in-person session scheduled, study staff will explain that they need to notify the partner of this decision and the cancellation of ongoing appointments. Withdrawal from the intervention will not impact either participant's ability to participate in the follow-up assessment, which will allow either partner to give feedback on what was appealing,

If a participant withdraws after completion of the treatment process (i.e., not wishing to participate in the follow-up assessments), the partner will not need to be informed, as all remaining study activities (assessment packet, interview process) are completed individually.

Involuntary withdrawal

Safety of participants/couple. Exclusion criteria was selected to minimize the likelihood that the intervention would negatively impact either partner. However, consistent with standard approaches in VA intervention research, we will withdraw participants due to unanticipated circumstances, such as extreme distress from participating in the intervention or if we judge the participation of the couple is not in their best interest. Any such decisions will be documented using the reporting guidelines (Section 6.0).

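### Sub-aim 2-1's four-score within-couple ANOVA cannot, as conventionally run, use a couple with one follow-up packet; a mixed model would, for a modest gain in precision and protection against baseline-related loss

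*Combined protocol and SAP*

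**What the plan says.** Section 5.6, Aim 2, recognises that partners' relationship quality and intimacy are dependent. For Sub-aim 2-1 it will "calculate effect size dyadically using a repeated measures ANOVA with Partner (Veteran-Supporting) and Time (pre-post" as within factors, and report partial eta-squared. Table 1 in Section 5.5 schedules the CSI and PRI at baseline and after treatment, so each couple contributes four scores per measure. Aim 2 effect sizes are then compared with one-month change "observed in past waitlist control studies of Veterans to inform power analysis".

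On expected loss, Section 5.6 states: "if we successfully recruit 20 couples, we expect to obtain complete data from 15 couples at follow-up".

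Follow-up is organised by individual. Under Section 5.1, each partner may complete the packet after the last session, mail it back, or keep it "to have as a reference when completing the questionnaires remotely in the final interview". For the interviews, "partners will be asked to schedule separate follow-up interviews with study staff". If a packet is late, "study staff will send reminder calls to participants to remind them to complete the packet" or offer completion by phone. Section 5.7 explains that a partner who withdraws after treatment does so without the other being told, because "all remaining study activities (assessment packet, interview process) are completed individually". It also leaves follow-up open to either partner when treatment is stopped early.

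Section 5.6 has no rule for a couple with one packet: no complete-case statement, no imputation and no likelihood-based model.

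**The concern.** The data collection allows one partner's follow-up to arrive without the other's, but the named analysis treats the couple as the unit and needs all four cells. By default, a packet that a participant completed and was paid for would not enter the Sub-aim 2-1 estimate.

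Two things are at stake. The first is precision: with about 15 complete couples, each unused packet counts. The second is bias: if the more distressed partners or couples are less likely to return, the complete couples are a selected group, and the effect size carried into planning the larger trial is shifted. The scores already collected could correct that.

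Sub-aims 2-2 and 2-3 are not affected in this way, because they use a separate Cohen's *d* for Veterans and for supporting partners and do not need both partners' data.

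**Working it through.** **Inputs from the documents.** 20 couples; 75% retention; four scores per couple (two partners, two times).

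**The plan's own figure.** 20 × 0.75 = 15 complete couples, which reproduces. So 5 couples are incomplete. Let k be the number of these with exactly one follow-up packet; k is not given and may be 0 to 5.

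**Assumed, not in the documents.** SD 1 at each time, pre-post correlation 0.7, same-time partner correlation 0.5, cross-partner cross-time correlation 0.7 × 0.5 = 0.35, and a true change of 0.30 SD.

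**Complete couples only.**
- Variance of one partner's change: 2(1 − 0.7) = 0.60.
- Covariance of the two changes: 2(0.5 − 0.35) = 0.30, so their correlation is 0.30/0.60 = 0.5.
- Variance of the couple-mean change: (0.60 + 0.60 + 2 × 0.30)/4 = 0.45.
- SE with 15 couples: √(0.45/15) = 0.173.

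**Hand check of the gain, change scores only.** With 15 complete and k half-observed couples split evenly by role, and ρ the correlation of the partners' changes, equivalent couples = 15 + (k/2)(1 + ρ). At ρ = 0.5:
- k = 0: 15.0, gain 0%.
- k = 2: 15 + 1.5 = 16.5, gain 10%.
- k = 5: 15 + 3.75 = 18.75, gain 25%.

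With k = 5, the gain is 16.7% at ρ = 0, 21.7% at ρ = 0.3, and approaches 33.3% as ρ approaches 1.

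**All four scores, baselines kept for every couple.** The first row takes the covariance as known (generalised least squares). The second gives approximate simulation results with an estimated unstructured covariance.

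| k | 0 | 1 | 2 | 3 | 4 | 5 |
|---|---|---|---|---|---|---|
| Covariance known | 3.9% | 8.5% | 13.0% | 17.4% | 21.8% | 26.2% |
| Covariance estimated | about 0% | 4–5% | 9% | 14–16% | 18–21% | 22–26% |

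The first row is the ceiling for these correlations. Over pre-post correlations of 0.5 to 0.8 and partner correlations of 0.3 to 0.7, the ceiling with k = 5 is about 23 to 30%.

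**In interval terms.** The mean simulated 95% CI half-width is 0.365 SD with complete couples, 0.337 with k = 2 and 0.319 with k = 5.

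**Bias (true value 0.30; 75% of couples complete).** Paired figures are for loss correlated 0.3 and 0.5 with the stated driver.

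| Driver of loss | Who is lost | Complete couples | Mixed model |
|---|---|---|---|
| Baseline distress | Individuals | 0.266 / 0.244 | 0.299 / 0.300 |
| Baseline distress | Whole couples | 0.269 / 0.241 | 0.302 / 0.297 |
| Poor response | Individuals | 0.388 / 0.442 | 0.340 / 0.371 |
| Poor response | Whole couples | 0.384 / 0.443 | 0.372 / 0.423 |

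For whole-couple loss driven by baseline distress, root mean squared error does not improve: 0.178 / 0.184 with complete couples against 0.179 / 0.183 with the model. For response-driven loss, the share of bias remaining is 0.071/0.142 = 50% for individuals and 0.123/0.143 = 86% for whole couples, at the stronger correlation.

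**The case against.** **Dropping is not a stated rule.** A reader might infer that the protocol directs one-packet couples to be discarded. It does not. Dropping is how this ANOVA conventionally behaves, and the plan is silent on missing data. This stands, and the point is worded accordingly.

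**Half-observed couples may be few.** Section 5.7 says that "if either partner withdraws during the treatment process, then the other partner will not be able to complete the treatment", which makes joint loss plausible, and reminder calls and phone completion limit loss of either kind. This stands too: with joint random loss the gain is about nil. But separate follow-up, and separate withdrawal decisions after treatment, mean that one-packet couples cannot be ruled out.

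**The percentages rest on assumptions.** A reader might take 22% as the expected gain or as its upper limit. It is neither. The documents give no correlations and no count of half-observed couples, and other plausible correlations put the ceiling with five such couples anywhere from about 23 to 30%.

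**The model is heavy for this sample.** An unstructured covariance has 10 parameters for 20 couples. The fits behind the figures were on normal data with equal variances. Section 5.4 requires only one partner to be distressed and only the Veteran to screen positive, so variances may differ by role. This is a fair reason to name a fallback, but not to keep an analysis that ignores collected data.

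**Little depends on the estimate.** The sample size rests on capacity, and no test or threshold uses this effect size. That limits the importance of the point.

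**Conclusion.** The point holds as a low-cost improvement, to be considered rather than required. The Sub-aim 2-1 analysis, as conventionally run, cannot use a follow-up packet whose counterpart is missing. The protocol's procedures can produce such packets, and the plan does not say how they would be handled.

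Under the assumed correlations (pre-post 0.7, partner 0.5), a mixed model gains about nil in precision if partners are lost together at random, about 9% with two half-observed couples, and about 22 to 26% if all five are half-observed. It removes bias only where loss depends on observed scores; where loss depends on unobserved response, half or more of the bias remained at the stronger correlation examined. The estimate stays imprecise either way, with a half-width of roughly 0.32 to 0.37 SD.

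A reader might go further and infer that the pilot is undersized or its feasibility aims compromised. The documents do not support that: there is no power target, and Aim 1 does not use this analysis.

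**What to change.** For the CSI and PRI under Sub-aim 2-1 only:

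- Replace the ANOVA with a linear mixed model containing role, time and role × time, an unstructured within-couple covariance, and REML with Kenward-Roger or Satterthwaite degrees of freedom. Use all observed scores from every couple with baseline data.
- Name in advance a simpler fallback covariance that allows unequal variances by role, for use if the model does not converge.
- Report the pre-post change divided by the baseline SD, with a 95% CI. The standardiser must be named: under the assumptions above, 0.30 baseline SD is 0.30/√0.60 = 0.39 individual change SD or 0.30/√0.45 = 0.45 couple-mean change SD. That difference would distort the comparison with waitlist studies.
- If partial eta-squared is still wanted, derive it as F/(F + df), with df the denominator degrees of freedom.
- Show the complete-couple result alongside, with the numbers of complete, half-observed and fully lost couples.
- State that the model corrects only for loss that depends on observed scores. Any sensitivity shift for other loss should be labelled arbitrary, since the documents give no basis for its size.

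**Cost.** Analysis wording only, with no new data. Partial eta-squared is no longer a direct output and rests on approximate degrees of freedom. A 10-parameter covariance fitted to 20 couples may fail on bounded or skewed scores, which is why the fallback is needed.
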